In 2010, we conducted a retrospective review of 4 cases and found that BLUSA tracheostomy helped facilitate communication in this unique population (IRB #: NA_00041547). Now, we would like to formally conduct a prospective study to evaluate the outcomes of patients using a BLUSA using a pretest-posttest research design.

Identifying the predictors of intelligibility and the impact of BLUSA on Quality of Life (QOL) and communication will promote communication between patients and healthcare providers. This empowers patients and allows healthcare staff to obtain a more accurate assessment of patients’ condition and tailor care accordingly.

2. Objectives (include all primary and secondary objectives)

Specific Aim 1: Determine the impact of a BLUSA on QOL in patients requiring prolonged mechanical ventilation in the hospital

Hypothesis 1a: The mean health-related QOL scores of patients who use BLUSA will be significantly higher compared to patients who do not use BLUSA.

Hypothesis 1b: The mean voice-related QOL scores of patients who use BLUSA will be significantly higher compared to patients who do not use BLUSA.

Specific Aim 2: Determine the outcomes of communication following the use of BLUSA in patients requiring prolonged mechanical ventilation in the hospital.

Hypothesis 2: Effectiveness of communication in patients who use BLUSA will be significantly improved compared to patients who do not use BLUSA.

Research Question 2a: What is the time to speech among patients who are unable to speak using a speaking valve?

Research Question 2b: What is the frequency and duration of speech with use of BLUSA?

Specific Aim 3: Identify the predictors of intelligibility in patients requiring prolonged mechanical ventilation in the hospital.

Hypothesis 3: Several factors such as age, sex, educational level, primary diagnosis, indications for mechanical ventilation, indication for tracheostomy, co-morbidities, and severity of illness will significantly contribute to speech intelligibility in patients requiring prolonged mechanical ventilation in the hospital.

Specific Aim 4: Validate the speech item in the health-related QOL instrument to evaluate speech as a domain of QOL in patients requiring prolonged mechanical ventilation in the hospital

Hypothesis 4: The mean health-related QOL scores will moderately correlate negatively with mean voice-related QOL (VR-QOL) questionnaire (criterion validity).

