- a) The BLUSA trial involves placement of a BLUSA tracheostomy tube by respiratory therapist after obtaining an order from an authorized prescriber (MD, PA, or NP). The SLP sets up the tracheostomy tube for speech and then determines the optimal air flow required for voicing. This amount of air flow is communicated to the ICU staff for further use.
- b) We will ensure that the SLP meets with the patient for a minimum of 3 sessions within a week to optimize the use of a BLUSA.
 - i. SLP will also assess the duration of successful speech during each session
 - ii. Sentence intelligibility will also be assessed during the 3rd session. This session will be audio-taped and reviewed by a second rater for sentence intelligibility.
 - iii. SLP will determine the level of independence with BLUSA during the 3rd session.

Control Group:

- a) This group will also receive BLUSA trial as standard of care but a week later after the pre and post assessments have been completed

C. Post-Assessment

[figure not shown]
1. Electronic Patient Records (POE, EPR, or EPIC)
 - a. Patient Characteristics
 - i. Severity of Illness
 - b. Patient Outcomes
 - i. Time to BLUSA in days
 - ii. Time between speaking valve trial and BLUSA
2. Patient Survey
 - a. Quality of life
 - b. Voice-Related Quality of life
 - c. Level of independence to use of BLUSA
 - d. Patient satisfaction to use of BLUSA

Setting: All vented units at the Johns Hopkins Hospital (MICU, SICU, CICU, CCU, NCCU, WICU, Wbg 5D, Wbg 5C & MPCU)

Instruments:

Name	Concept measured	Number of items
QOL-MV	Quality of life in mechanically ventilated patients questionnaire	12
VR-QOL	Voice-related quality of life questionnaire	10
SIT	Sentence intelligibility test	11
SOFA	Sequential Organ Failure Assessment Tool	6
RASS	Richmond Agitation Sedation Scale	1
CAM-ICU	Confusion Assessment Method	4
Additional questions	Demographic Data Patient's independence and satisfaction with BLUSA	2

Study Protocol Flow Chart

Date: 12/19/2013

Principal Investigator: [name]

Application Number: NA_00086689

- b. Study duration and number of study visits required of research participants.
The study duration is estimated to be approximately 2 weeks per patient with a total of 5 visits by study team.
- c. Blinding, including justification for blinding or not blinding the trial, if applicable. Patients will not be blinded to intervention or control group.

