 1. Sentence intelligibility
 2. Level of independence with BLUSA
 3. Patient satisfaction with BLUSA
- c) Variables of Interest
 1. Age, Sex, Race
 2. Indication for ICU admission
 3. Indication for Tracheostomy
 4. Severity of Illness (measured by SOFA scores)
 5. Delirium (CAM-ICU)
 6. Sedation (RASS)
 7. Motor Speech (Cranial nerve assessment V, VII, IX, X, and XII)
 8. Information about secretions (suction frequency, secretion quality and quantity)
 9. Time to SLP consult in days
 10. Time to initial in-line speaking valve trial
 11. Severity of Illness
 12. Time to BLUSA in days
 13. Time between speaking valve trial and BLUSA

d) Statistical plan including sample size justification and interim data analysis.

In order to compare changes in health-related quality of life from pre-assessment to post-assessment, we need 73 participants in each group. This allows for a 20% drop out rate and is based on a sample size of 61 individuals in each group to achieve 80% power and a clinically meaningful 20% increase in health-related QOL mean score from 61.16 (SD \pm 21.74) to 73.38 (SD \pm 26.09) based on another "Quality of Life in Mechanically Ventilated Patients" study by PI. We assume a two-tailed test with a significance level of $\alpha = 0.05$.

Interim data analysis will be conducted after 12 months of data collection. Mean, standard deviation, median and inter-quartile range will be calculated for continuous variables. Paired t-tests will be used to compare pre and post assessment scores for continuous variables. Frequencies and percentages will be calculated for categorical variables. Chi square and Fisher Exact tests will be used to compare pre and post assessment scores of categorical variables. Validation of the QOL instrument will include calculation of Cronbach's alpha, Pearson correlation, Kappa.

e) Early stopping rules.

Reasons for stopping data collection for a participant will include

1. change in clinical condition
2. discharge from the hospital

8. Risks

a. Medical risks, listing all procedures, their major and minor risks and expected frequency.

Administration of questionnaires repeatedly can be burdensome. In addition, questions about their quality of life while mechanically ventilated may be emotionally distressing.

b. Steps taken to minimize the risks.

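### No test compares BLUSA with control: Section 7d names only paired pre-versus-post t-tests, while Hypotheses 1a and 1b are between-group

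*Combined protocol and SAP*

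**What the plan says.** Section 2 states both quality-of-life hypotheses as contrasts between groups. For 1a: "The mean health-related QOL scores of patients who use BLUSA will be significantly higher compared to patients who do not use BLUSA". For 1b: "The mean voice-related QOL scores of patients who use BLUSA will be significantly higher compared to patients who do not use BLUSA". Section 7a makes quality of life the primary outcome.

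Section 4a sets up an intervention group and a delayed-device control group. On the controls it says: "This group will also receive BLUSA trial as standard of care but a week later after the pre and post assessments have been completed".

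Section 7d sizes the trial per group but words the purpose as pre to post: "In order to compare changes in health-related quality of life from pre-assessment to post-assessment, we need 73 participants in each group". It continues: "This allows for a 20% drop out rate and is based on a sample size of 61 individuals in each group". The target is a "clinically meaningful 20% increase in health-related QOL mean score from 61.16" (SD 21.74) to 73.38 (SD 26.09), with 80% power and two-sided alpha 0.05.

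The next paragraph opens with "Interim data analysis will be conducted after 12 months of data collection" and then gives the only test for continuous scores: "Paired t-tests will be used to compare pre and post assessment scores for continuous variables". The chi-square and Fisher tests are also described as pre versus post. Cronbach's alpha, Pearson correlation and kappa are assigned to validating the instrument.

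**The concern.** The named test answers a different question from the hypotheses. A paired t-test asks whether scores moved within a group; Hypotheses 1a and 1b ask whether BLUSA patients do better than controls. Running the paired test in both arms does not help, because two separate within-arm results do not test the difference between arms.

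The paired-test sentence follows the interim-analysis sentence, so it may describe the interim look, the final analysis or both. On every reading no between-group test is named. If it covers the interim look only, no final test is named at all.

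These are hospitalised, ventilated patients assessed about a week apart, so scores could move for reasons unrelated to the tube. A general rise would be credited to BLUSA and a general fall would hide a benefit. The control group can separate the two only if the arms are compared. Leaving the test open also allows the choice among several candidates of differing power to be made after the data are seen.

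**Working it through.** **Inputs from Section 7d.** Means 61.16 and 73.38 (difference 12.22), SDs 21.74 and 26.09, two-sided alpha 0.05, power 80%, 61 evaluable and 73 enrolled per group, 20% dropout. Evaluable after dropout: 73 × 0.8 = 58.4, taken as 58. **Assumed, because the documents do not give them:** the pre-post correlation r and the general drift over the week.

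**1. Reproduce the 61.**
Two independent means: n = (1.96 + 0.8416)² × (21.74² + 26.09²) / 12.22² = 7.849 × 1153.3 / 149.33 = 60.6, so 61 per group.
Paired: n = 7.849 × (1153.3 − 2r × 21.74 × 26.09) / 149.33.

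| r | 0 | 0.2 | 0.3 | 0.5 | 0.7 |
|---|---|---|---|---|---|
| paired n | 60.6 | 48.7 | 42.7 | 30.8 | 18.9 |

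The stated 61 fits a two-group comparison. It fits a paired one only at zero correlation. This supports a between-group intent but does not prove it, since the sentence itself uses pre/post wording.

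**2. No device effect, general rise.** Chance that the BLUSA arm's paired test favours BLUSA: noncentral t, 57 df, upper tail, SD of change = 21.74 × √(2(1 − r)), n = 58.

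| General rise (points) | 0 | 1 | 2 | 3 | 5 |
|---|---|---|---|---|---|
| r = 0.3 | 2.5% | 5% | 8% | 14% | 31% |
| r = 0.5 | 2.5% | 5% | 10% | 18% | 41% |
| r = 0.7 | 2.5% | 6.5% | 14% | 27% | 60% |

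At n = 61 the figures are at most about 2 points higher. If a reader took a significant BLUSA arm beside a non-significant control arm as benefit, a rule the plan does not state, the chance is p(1 − p): 2.4%, 5%, 9%, 15% and 24% at r = 0.5.

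A drift common to both arms cancels in a between-group test. In simulation (20,000 runs per setting; drift 0 or 5; r = 0.3, 0.5, 0.7; groups comparable at baseline), ANCOVA, change-score and post-mean tests favoured BLUSA wrongly in 2.2% to 2.7% of runs.

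**3. True effect 12.22, with and without a general fall of 5 points.** Paired test in the BLUSA arm: variance of change 1153.3 − 2r × 21.74 × 26.09, n = 58; net mean change is 12.22 − 5 = 7.22 with the fall. ANCOVA is unaffected by a common fall.

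| r | Paired, fall of 5 | Paired, no drift | ANCOVA |
|---|---|---|---|
| 0.3 | 47% | 89% | 82% |
| 0.5 | 61% | 97% | 88% |
| 0.7 | 81% | 99.8% | 97% |

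**4. Power of the between-group options** (normal approximation; pre SD 21.74 in both arms; post SD 26.09 on BLUSA and 21.74 on control; common ANCOVA slope), shown as 58 / 61 per arm.

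| r | Post means | ANCOVA | Change scores |
|---|---|---|---|
| 0.2 | 78% / 80% | 80% / 82% | 62% / 64% |
| 0.3 | 78% / 80% | 82% / 84% | 68% / 70% |
| 0.5 | 78% / 80% | 88% / 90% | 82% / 83% |

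At r = 0 ANCOVA equals post means. Calculations based on the t distribution lie within 1 point. Change scores fall below 80% power when r is under about 0.46 (61 per arm) or 0.48 to 0.49 (58 per arm). ANCOVA with 58 per arm reaches 80% at r of about 0.21 to 0.24.

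**The case against.** The best defence is that a group comparison is plainly meant: the hypotheses state it, the control group is built for it, the sample size is per group, and 61 matches a two-sample calculation. The paired-test sentence does not exclude such a comparison, and the document is a short IRB form for a study that calls itself a pilot. Most of this stands, and the gap does look like an omission rather than a deliberate choice. But intent does not name a test, three different tests fit the text, and a trial sized for 80% power at alpha 0.05 is testing hypotheses whatever its label.

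The drift figures rest on assumptions, and with no drift the paired test has more power than ANCOVA (step 3). Both points stand. They show why the numbers are illustrations; they do not make the paired test answer Hypothesis 1a.

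ANCOVA is a preference, which is accepted: either alternative would also close the gap. It is also fair that Section 7a says only quality of life, so treating Hypothesis 1a as the primary comparison is an inference, supported by the sample-size sentence.

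The flow chart is not visible, but it sits under study procedures and nothing suggests it holds an analysis method.

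**Conclusion.** The concern holds and should be fixed before analysis. As written, the health-related QOL comparison and Hypothesis 1b have no test, and the one test named for continuous scores cannot separate a device effect from general change. This follows from the text alone and needs no assumed figure.

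The size depends on drift and r, both unknown. There is no inflation at zero drift. With 58 per arm and r from 0.3 to 0.7, one-sided error runs from 8% to 14% for a 2-point general rise and from 31% to 60% for a 5-point rise, against 2.5%. The near-2.5% rate for between-group tests assumes groups comparable at baseline, and the visible text gives no allocation method.

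**What to change.** Name one between-group primary test for the final analysis. Suggested wording: *Post-assessment QOL-MV will be compared between the BLUSA and control groups by ANCOVA adjusted for pre-assessment QOL-MV (two-sided alpha 0.05), reporting the adjusted difference and 95% CI. VR-QOL will be analysed in the same way. Paired t-tests will describe change within each group.*

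Two alternatives are valid. A two-sample t-test of post-assessment means fits Hypothesis 1a and the 60.6 but gains nothing from the baseline score. A two-sample test of change fits the sample-size wording but loses power at low r (step 4).

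Also:
- Say whether the paired tests belong to the interim look, the final analysis or both.
- State how patients are allocated. If not at random, adjust for collected baseline factors such as SOFA and limit causal wording.
- Confirm the VR-QOL scoring direction. Hypotheses 1a and 1b both predict higher scores, while Hypothesis 4 predicts a negative correlation between the two measures.
- Name a between-group test for Hypothesis 2, which has the same gap.

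The cost is a few sentences, using QOL-MV, VR-QOL and SOFA data already planned. Naming the test needs no extra patients, but 80% power at low r depends on keeping about 61 evaluable per arm rather than 58. Wording cannot remove confounding. With a 5-point baseline gap that persists, no device effect and 58 per arm, ANCOVA would wrongly favour BLUSA about 14%, 10% or 8% of the time at r = 0.3, 0.5, 0.7, and post means about 23%. Change scores stay near 2.5% there only because the gap is assumed constant.

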3. Background (briefly describe pre-clinical and clinical data, current experience with procedures, drug or device, and any other relevant information to justify the research)

1. Abstract from the prior study (IRB #: NA_00041547) that got accepted for publication in Journal of Medical Speech-Language Pathology:

Purpose: To describe the types of talking tracheostomy tubes available, present four case studies of critically ill patients who used a specialized tracheostomy tube to improve speech, discuss their advantages and disadvantages, propose patient selection criteria, and provide practical recommendations for medical care providers.

Method: Retrospective chart review of patients who underwent tracheostomy in 2010.

Results: Of the 220 patients who received a tracheostomy in 2010, 164 (74.55%) received a percutaneous tracheostomy and 56 (25.45%) received an open tracheostomy. Among the percutaneous tracheostomy patients, speech-language pathologists were consulted on 113 patients, 74 of whom were on a ventilator. Four of these 74 patients received a talking tracheostomy tube, and all four were able to speak successfully while on the mechanical ventilator even though they were unable to tolerate cuff deflation.

Conclusions: Talking tracheostomy tubes allow patients who are unable to tolerate cuff deflation to achieve phonation. Our experience with talking tracheostomy tubes suggests that clinicians should consider their use for patients who cannot tolerate cuff deflation.

2. Additionally, over the last couple of years, the use of BLUSA has increased dramatically at the Johns Hopkins Hospital.

4. Study Procedures

- a. Study design, including the sequence and timing of study procedures (Distinguish research procedures from those that are part of routine care).
Design: Prospective Pretest-Posttest design Clinical Trial – Pilot Study

Sequence and timing:

A. Pre – Assessment

1. Electronic Patient Records (POE, EPR, or EPIC)
 - a. Demographic Data
 - b. Patient Characteristics
 - c. Patient Outcomes
2. Patient Survey
 - a. Quality of life
 - b. Voice-Related quality of life

B. Intervention vs. Control Group

Intervention Group:

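### Section 7d names unpaired tests (chi-square, Fisher) for pre/post categorical comparisons in the same patients; their error rate is wrong when the two values are correlated, but the reach is narrow

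*Combined protocol and SAP*

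**What the plan says.** Section 4a describes the study as a "Prospective Pretest-Posttest design Clinical Trial – Pilot Study". Both arms are assessed twice. The control arm receives the device "a week later after the pre and post assessments have been completed", so its patients also supply a pre and a post value.

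Section 7d gives one rule for each type of variable. For continuous data: "Paired t-tests will be used to compare pre and post assessment scores for continuous variables". For categorical data: "Chi square and Fisher Exact tests will be used to compare pre and post assessment scores of categorical variables". Neither section 7d nor any other section names McNemar, marginal homogeneity, signed-rank or another paired method for categories. Kappa appears only for validating the quality-of-life instrument. The plan does not list which categorical variables are compared pre to post.

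**The concern.** Chi-square and Fisher tests of a change in proportion treat the pre values and the post values as coming from two separate sets of patients. Here they come from the same patients. The plan respects the pairing for continuous scores and drops it for categories, although the comparison is the same.

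The consequence depends on the sign of the within-patient correlation. If it is positive, the unpaired test overstates the variance of the change, rejects too rarely and can miss a real shift. If it is negative, the test understates the variance and rejects too often. At stake is any categorical variable that is measured at both times and analysed under this rule.

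**Working it through.** **The plan's own figure.** Section 7d states 61 per group for 80% power at two-sided 5%, for means of 61.16 and 73.38 with SDs of 21.74 and 26.09.
- Averaged variance: (21.74² + 26.09²)/2 = 576.7, so SD = 24.01. Difference: 12.22.
- n = 2 × 576.7 × (1.960 + 0.842)² / 12.22² = 60.6, rounded up to 61. This reproduces.
- 61 × 1.2 = 73.2, which gives the stated 73.

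Neither figure involves a categorical test. I use 61 only as a realistic number of pairs in one group.

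**Large-sample size.** Let the true proportion be p at both times and phi the within-patient correlation. The variance of the difference in proportions is 2p(1−p)(1−phi)/n. The chi-square test uses 2p(1−p)/n. The true size of a nominal 5% test is therefore 2[1 − Φ(1.96/√(1−phi))]:
- phi 0: 5.0%
- phi 0.3: 1.96/0.837 = 2.34, size 1.9%
- phi 0.5: 1.96/0.707 = 2.77, size 0.56%
- phi −0.3: 1.96/1.140 = 1.72, size 8.6%

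**Exact figures at 61 pairs.** The proportions and phi are my assumptions. The probability of yes at both times is p1·p2 + phi·√(p1(1−p1)p2(1−p2)). For 50% to 70% at phi 0.5 this is 0.35 + 0.5 × 0.229 = 0.465, which leaves discordant cells of 0.035 and 0.235. I summed the multinomial probabilities of all tables that each test rejects at 5%. Chi-square and Fisher are applied to the time-by-category table, without continuity correction for chi-square.

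Size, 50% at both times:

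| phi | Chi-square | Fisher | McNemar |
|---|---|---|---|
| −0.3 | 9.5% | 6.7% | 4.9% |
| 0 | 5.7% | 3.7% | 5.2% |
| 0.3 | 2.3% | 1.3% | 5.3% |
| 0.5 | 0.7% | 0.3% | 4.8% |

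Power, 50% to 70%:

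| phi | Chi-square | McNemar | Fisher | Exact McNemar |
|---|---|---|---|---|
| 0 | 63% | 62% | 56% | 53% |
| 0.3 | 65% | 78% | 57% | 70% |
| 0.5 | 68% | 90% | 58% | 86% |

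Simulation of the same set-up agrees to within about one percentage point. The departures from 5% at phi 0 reflect the discreteness of small tables, not the pairing.

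**The other way to run the rule.** A chi-square test on the pre-by-post cross-table tests association between the two assessments, not change. With 50% at both times and no change at all, it rejects in 65% of trials at phi 0.3 and 98% at phi 0.5. This layout does not rescue the sentence either.

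**Which variables the rule reaches.**
- Both quality-of-life measures are compared as means (section 2, hypotheses 1a and 1b), so they fall under the paired t-test.
- Sentence intelligibility is assessed at the third device session (section 4a).
- Independence and satisfaction with the device appear only in the post-assessment list (section 4a).
- Both questionnaires are given pre and post (section 4a), so their single items could be compared as categories. The plan does not say that they will be.

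**The case against.** The strongest objection is that the rule may apply to almost nothing. None of the three named secondary outcomes has a pre value in the text, and the primary outcome is continuous. This stands, and it limits the importance of the point. It does not make the sentence correct: the plan wrote a rule for such comparisons, and the rule is wrong for them.

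Delirium status is a tempting example, but a poor one. Section 5 excludes delirium at entry, so pre values should be nearly all negative. With 0 of 61 before and 5 of 61 after, Fisher gives p = 0.057 and exact McNemar 0.063. With 6 of 61 after, they give 0.027 and 0.031. Both cross 5% at the same count, so nothing is lost there.

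A reader might also infer that the tests always lose power, or that they generate false-positive claims. Neither holds in general. At phi 0 there is essentially no loss. Under positive correlation the tests are conservative, and inflation needs a negative correlation, which is unusual for repeated measures.

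Finally, the hypotheses under Aims 1 and 2 compare device users with non-users, and a within-group McNemar test does not address those. That is true. The correction only makes the within-group comparison valid.

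**Conclusion.** The rule is wrong as written for paired categorical data, and no other passage corrects it. For positive correlations of 0.3 to 0.5, 61 pairs and a shift from 50% to 70%, chi-square gives up about 13 to 22 points of power against McNemar (78 − 65 and 90 − 68). At phi −0.3 its size is nearly double the nominal 5%. These figures illustrate the mechanism under assumed proportions and correlations; they do not predict this trial's results.

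A reader might conclude that the main result or the sample size is compromised. The documents do not support that. The primary quality-of-life score is continuous and has a paired test, the 61 and 73 do not depend on categorical tests, and the post-only secondary outcomes are not compared with a pre value. The severity is minor.

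**What to change.** Edit the categorical sentence in section 7d:
- For within-group pre/post comparisons of binary variables, use McNemar, in its exact form when discordant pairs are few.
- For ordinal or multi-category variables, use the Wilcoxon signed-rank test or a test of marginal homogeneity.
- Keep chi-square and Fisher for intervention against control at one time point, which suits the post-only categorical outcomes.

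It would help to list the categorical variables measured at both times, so that the scope of the rule is clear. The cost is a sentence or two of text, with no extra patients, visits or data.
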